## 8.3 SAMPLE SIZE

Novel ureteric stent insertion:

50 patients (25 kidney stone patients, 25 oncology patients)

A sample of 50 participants will also allow us to estimate the stent failure rate with a 95% confidence interval (CI) width of approximately +/13%, or approximately +/-18% per arm, sufficient to judge whether the stent is sufficiently safe to progress to further testing. All participants who entered the trial will be included in the analysis of the primary endpoint and its components (intention to treat population). Anyone who consents and/or is registered on the database will be replaced if they do not begin the procedure for insertion of the stent. Those who receive the stent will be included in all other analyses (as-treated population), as these endpoints relate to characteristics of the stent or its use. Loss to follow up is expected to be low, so no adjustment has been made to the sample size. Withdrawal from the study prior to primary endpoint assessment is felt to be unlikely, but we will allow for an additional 3 participants to cover this possibility.

#### 8.4 INTERIM ANALYSIS

No formal statistical testing at an interim stage is planned. For both the kidney stone and oncology cohorts, there will be an assessment of safety after 10 participants have had the stent removed. There is a safety assessment after the 25 kidney stone patients and up to 15 oncology patients have had the stent removed. See section 3.1 for full details.

## 8.5 STATISTICAL ANALYSIS PLAN (SAP)

The primary analysis will be an estimate of the proportions (and associated 95% Wilson method confidence intervals [21] of stent failure, presented by patient group (oncology or kidney patients). This data will also be compared against data from those using existing stents (UPPEUS); an odds ratio and two-sided 95% confidence interval will be produced for oncology patients and kidney stone patients separately to compare the proportions of stent failure according to stent type. Each element of the composite outcome will also be presented and compared as a secondary analysis, using the same methods as the primary endpoint. The EQ-5D-5L, USSQ, and USI-QoL scores will be summarised with mean, SD, median, and IRQ. No corrections for multiple testing will be applied, and no threshold is set for the p-value as the study is not designed to formally compare groups. Descriptive statistics will be presented for baseline measures and the other secondary outcomes:

- Dwell time (mean, standard deviation) and number of stents required over clinically meaningful period
- Patients who: experience urinary symptoms (for any and for each symptom), use antibiotics, are readmitted, have urosepsis, die (frequency and percentage)
- Questionnaires at each time point (mean and standard deviation or median and quartiles)
- Laboratory and microbiology data at each time point (mean and standard deviation or median and quartiles)

Adverse events and Serious Adverse Events for the full population will be summarised descriptively for both groups. Overall AEs will be also summarised by CTCAE Grade for each group. No statistical comparisons will be undertaken on this data.

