Considering only onco-urological patients, >30,000 stents are inserted every year across 200 NHS units. Due to stent failures, each patient undergoes 3 to 6 replacements, resulting in >90,000 stent replacements. Under the current tariff-based system, hospitals are paid for each intervention, costing the NHS >£3,500, bringing the total cost of replacements to ~£315m annually. Unnecessary replacements increase the number of bednights and use of anaesthetics. A longer-lasting stent means that each patient comes to the hospital ideally only once, reducing their exposure to the hospital environment and anaesthetic-associated risks. Additionally, under the current model hospitals would improve their quality of service and save at least 2 bed-nights per patient. The NHS is moving towards a "block contract" model, meaning that hospitals will receive a lump sum for the year, and they'll regularly monitor budgets and improve cost efficiency where possible. Improved stents will allow the same urology budget to deliver more healthcare, reducing theatre time for stent insertion and replacement. Our innovative stent design offers a potential annual saving of >£210m for the NHS, allowing hospitals to reallocate their resources. Today E&B is still a major determinant of stent failure and associated side effects. We aim to address this challenge through our novel stent, and if equivalent safety and improved efficacy are demonstrated, anticipate market launch via third-party suppliers 2-3 years post project.

Solutions to break this pathway (stent presence leading to inflammation, pain and infection) have been developed, including stent construction materials (e.g. metallic alloys, polymers, biodegradable and drug-eluting materials), stent coatings (e.g. heparin, chitosan, hydrogel, carbon) and alternative stent shapes (e.g. double-J, loop, mesh, string, expandable), to improve the efficacy and safety of stents [10]–[13]. Despite all these advances, there is still a significant prevalence of E&B [14]–[16]. This is also due to the lack of studies correlating fluid dynamic metrics with deposition of particles causing E&B. The lead applicant's PhD

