## 2.2 PRIMARY TRIAL OBJECTIVE AND ENDPOINT

The primary endpoint is stent failure, defined as any of:

- a) a stent change earlier than planned (oncology only);
- b) need for stent related additional surgical or radiological intervention;
- c) kidney failure and/or worsening hydronephrosis.

No intercurrent events (events that would affect the collection or interpretation of stent failure data) are thought likely to occur.

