## 2.5 TABLE OF ENDPOINT/OUTCOMES

	Objective	Outcome Measures	Summary method(s)
Primary	To determine rates of stent failure	Stent failure, defined as any of: a) a stent change earlier than planned (oncology only); b) need for stent related additional surgical or radiological intervention; c) kidney failure (evidenced by acute kidney injury (AKI) on blood tests (eGFR or creatinine kidney function tests) and/or worsening hydronephrosis on imaging	Frequency and percentage of people experiencing any stent failure
Secondary	To assess extent of encrustation and biofilm (E&B)	
 
Cell culturing (CFU counts per ml per bacterial microorganism)
 
Dwell time
 
Imaging (selected samples of stents will be examined using non-contact, non-destructive episcopic-differential-interference-contrast (EDIC) microscopy allowing imaging of the surface with the biofilm in-
 
	
 
Mean and standard deviation or median
 
Absolute value (Days)
 

		situ and colonisation by bacteria – when needed).	
	To determine whether the novel stent leads to better clinical outcomes	
 
Individual component of the primary outcome
 
Urinary symptoms
 
Infections
 
	
 
As per primary outcome
 
Frequency and percentage of participants experiencing each symptom
 
Frequency and percentage of people with antibiotic
 
use, readmission, urosepsis, ITU, death; number of infections per
 

	To assess impact of the novel ureteric stent on quality of life	Questionnaires at:      Baseline     While stent is in situ     Post-surgery	unit of time stent is in use Appropriate descriptive summaries (e.g., median and quartiles) per timepoint
	To understand patient experience in having the novel ureteric stent inserted and reason for participation in the trial	30–45-minute Qualitative interviews with Oncology and Kidney stone cohorts	An inductive thematic analysis of interview transcripts
Exploratory	To assess extent of encrustation and biofilm (E&B)	Weight: Stents will be weighed post-removal upon arrival at the microbiology lab	Mean and standard deviation or median and quartiles of weights pre- and post-insertion

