#### 3 OVERALL TRIAL DESIGN

Two single-arm, multicentre, unblinded, first-in-human trials to investigate a novel ureteric stent in 1) patients with kidney stones and 2) oncology patients. The two separate arms will run simultaneously, with a stopping point to assess the safety of the stent in the Kidney Stone cohort, before the Oncology cohort recruitment commences. This is an early phase trial to assess whether this stent can be inserted and does not have discernible difference in failure or symptoms in patients who have "lived experience" with a previous (market standard) ureteric stent. Each single-arm trial runs in two phases, with a pause to assess safety, and recruitment to the oncology cohort will only occur following safety review for the kidney stone cohort. A qualitative sub study will also be carried out across the two arms. A control group is not included as the aim of the trial is to generate initial first-in-human data to support further development and testing of the novel ureteric stent. Data from a (partly) contemporaneous study (UPPEUS) will be used to support this decision. The design is aligned with the IDEAL framework (designed for novel surgical interventions), and specifically phase 2a of the development process [20]

Kidney stone patients and oncology patients admitted to either the University Hospital Southampton (UHS) or University College London Hospital (UCLH) for management of kidney stones or for the management of urine drainage in ureter will have a novel ureteric stent instead of a conventional stent. The novel ureteric stent will be removed or replaced within 4 weeks (kidney stone patients) or ~25 weeks (oncology patients). Recruitment to the cohort of oncology patients will only commence after a safety review of 10 kidney stone patients have taken place.

The Kidney stone patients will be assessed for safety signals after 10 and 25 patients have had the novel ureteric stents removed (<4 weeks after insertion). Recruitment will continue while the analysis of the first 10 patients takes place. Stopping rules after 10 and 25 patients are summarised in Table 1 below.

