#### 5.3 INCLUSION CRITERIA

- 1. Aged 18 years or over
- 2. Ureteric stents clinically indicated either due to kidney stones or abdominal/pelvic cancers compressing ureters
- 3. Previous lived experience with ureteric stents

should inform the patients new healthcare professional.

- 4. Awaiting insersion/replacement of stents
- 5. Ability to give consent
- 6. Ability to interact with online and written study documentation
- 7. Sufficient English to complete study documentation and questionnaires

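### The oncology odds ratio against UPPEUS compares raw failure proportions with no common time horizon, so it reflects stent type only if time at risk is similar in both studies

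*Protocol*

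**What the plan says.** Protocol section 8.5 makes the estimated failure proportion in each cohort, with a Wilson 95% interval, the primary analysis. It then adds a comparison with patients who had existing stents in UPPEUS: "an odds ratio and two-sided 95% confidence interval will be produced for oncology patients and kidney stone patients separately", with the purpose "to compare the proportions of stent failure according to stent type". Section 2.5 summarises the endpoint as "Frequency and percentage of people experiencing any stent failure". Neither section sets a time by which failure is counted.

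Time at risk comes from other sections:
- Section 3: "The novel ureteric stent will be removed or replaced within 4 weeks (kidney stone patients) or ~25 weeks (oncology patients").
- Section 6.6.5 lets the treating clinician remove an oncology stent sooner.
- Section 6.8.1 counts removal because the stent is no longer needed as a success, however early it happens.
- Section 5.4 excludes only patients expected to survive less than 4 months.
- Section 2.2, component (a), is "a stent change earlier than planned (oncology only"), so its window is set by the planned date.

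Section 3 explains the lack of a control group and adds: "Data from a (partly) contemporaneous study (UPPEUS) will be used to support this decision". The dwell time, size and failure rate of UPPEUS are not stated. Section 8.5 also says that the study is not designed for formal group comparison and sets no p-value threshold.

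**The concern.** An odds ratio of 1 here means that the same share of patients ever failed in the two studies. That equals no difference between stents only if the stents were at risk for similar lengths of time in similar patients. A longer time in place gives more chance to fail with any stent. A later planned date also widens the window in which a change counts as early.

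The protocol takes account of exposure for infections, which section 2.5 summarises per unit of time in use, but not for its primary endpoint. If UPPEUS stents were in place for less time, an equally good novel stent would look worse and a real benefit could be masked. If they were in place for longer, the novel stent would look better and harm could be masked. The point is confined to oncology, where dwell is long and component (a) applies.

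**Working it through.** **The plan's own figure.** Section 8.3 gives a precision of about ±13% for 50 patients and ±18% for 25. The Wilson half-width is z/(1+z²/n) × √[p(1−p)/n + z²/(4n²)]. For p from 0.4 to 0.5 it is 13.1% to 13.4% (n=50) and 17.9% to 18.3% (n=25). The simpler Wald formula at p = 0.3 gives 12.7% and 18.0%. The stated precision reproduces, and this concern does not touch it.

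**Inputs for the illustration.**
- CASSETTE oncology dwell: 25 weeks (section 3).
- Comparator dwell T: not given, so varied.
- Failure by 25 weeks, p: assumed 10% to 50%.
- Hazard: assumed constant and equal for both stents, so there is no stent effect.

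**Formula.** Hazard h = −ln(1−p)/25. Comparator failure q = 1 − exp(−hT). OR = [p/(1−p)] / [q/(1−q)].

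**Example, p = 0.30.** h = 0.3567/25 = 0.01427 per week.
- T = 13: q = 1 − exp(−0.1855) = 0.169; OR = 0.4286/0.2038 = 2.10.
- T = 26: q = 1 − exp(−0.3709) = 0.310; OR = 0.4286/0.4491 = 0.95.

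Odds ratio, novel versus conventional, for equally good stents:

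| Comparator dwell (weeks) | p = 10% | p = 30% | p = 50% |
|---|---|---|---|
| 13 | 1.97 | 2.10 | 2.30 |
| 16 | 1.59 | 1.67 | 1.79 |
| 20 | 1.26 | 1.30 | 1.35 |
| 25 | 1.00 | 1.00 | 1.00 |
| 26 | 0.96 | 0.95 | 0.95 |
| 30 | 0.82 | 0.80 | 0.77 |
| 39 | 0.62 | 0.58 | 0.51 |

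**A better stent can look the same.** Halving the hazard over 25 weeks gives a cumulative hazard of (h/2) × 25 = 12.5h. A conventional stent left for 12.5 weeks accumulates the same amount, so the odds ratio is 1.0.

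**Which time-adjusted measure.** Cumulative failure at one common time is equal for equal stents whatever the shape of the hazard. A rate per stent-week gives 1.00 only when the hazard is constant. Take a rising hazard (Weibull shape 2, 30% failure by 25 weeks, 25 against 13 weeks):
- Comparator cumulative hazard = 0.3567 × (13/25)² = 0.0964, so q = 0.092.
- Expected weeks at risk are 22.3 and 12.6.
- Rates are 0.30/22.3 = 0.0134 and 0.092/12.6 = 0.0073, a ratio of 1.84 with no stent effect.

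Shape 1.5 gives 1.36. The rate ratio should therefore not be the main measure.

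**The case against.** The strongest reply is that nothing in the protocol shows a different dwell in UPPEUS. Section 4.4 describes advice given as standard care for any stent, with dwell under 6 months. That is close to CASSETTE's 25 weeks, and at 26 weeks the distortion is negligible. This stands: the bias is conditional in existence, sign and size.

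A reader might infer a shorter conventional dwell from section 1.1: "Due to stent failures, each patient undergoes 3 to 6 replacements". The annual cost there (30,000 × 3 × £3,500 = £315m) suggests a yearly count, hence roughly 52/6 = 8.7 to 52/3 = 17.3 weeks per stent. The inference fails. On the protocol's own words those intervals are cut short by failure, so they describe the outcome and not a planned end of exposure. If conventional stents were planned for 25 weeks (assumed) and stayed 17.3, 13 or 8.7 weeks on average because they failed, a constant hazard implies 54%, 77% or 93% failure. A raw odds ratio would then be showing a real difference. The sentence is also not about UPPEUS.

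It is also fair that the comparison is not a formal test, so false-positive rates and power are the wrong yardstick. Section 8.3 ties the judgement on further testing to the single-arm interval. That lowers the stakes, but a descriptive estimate can mislead in the same way.

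Failure per stent over its planned use is a legitimate target too, but it is not an effect of stent type when plans differ. The inclusion criterion "Previous lived experience with ureteric stents" raises a question of patient mix. Restricting UPPEUS to match it, and aligning the failure definitions, can be left to the statistical analysis plan, which is not at hand.

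**Conclusion.** The concern holds in conditional form. The protocol itself fixes an odds ratio of raw proportions and ties it to stent type, so this is not a detail merely left open. That reading is sound only if oncology time at risk is similar in UPPEUS. With 30% failure by 25 weeks and equal constant hazards, the no-effect odds ratio is 2.1 at a 13-week comparator dwell, 1.00 at 25 weeks, about 0.95 at 26 and 0.58 at 39. These are illustrations on assumed inputs, not estimates of the actual bias.

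The documents do not support saying that the comparison is biased against the novel stent, because UPPEUS dwell is not given. The single-arm Wilson estimates stand, and they carry most of the progression judgement. UPPEUS has a supporting role, and the change is worth making because it protects that role in either direction.

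**What to change.** In section 8.5, for the oncology cohort:

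1. Add a comparison of cumulative failure at a common time point that lies within both studies' dwell times, by Kaplan-Meier or cumulative incidence. Planned removal, or removal because the stent is no longer needed, ends time at risk; death is a competing event. A time point before the planned dates also gives component (a) the same window in both studies. A hazard ratio over the shared period is an alternative.
2. Use a rate per stent-week only as a sensitivity analysis, since it assumes a constant hazard.
3. Report planned and actual dwell in both studies.
4. Keep the raw odds ratio as descriptive, and call it a between-study comparison.

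Cost: a wording change and slightly more analysis. CASSETTE already collects dwell time in days. UPPEUS insertion and removal dates must be obtained. If they are not available, the odds ratio should carry a plain caveat on time at risk.
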